6.3. Screening, Retesting, and Screen Failures

6.3.1. Screening

Once informed consent is obtained, screening assessments can occur. At this time, a unique identification number is assigned that will be used on study-related documents pertaining to the participant. Any identification numbers that are assigned will not be reused even if the participant does not receive treatment or continue in the study. Study sites are required to document all screened participants initially considered for inclusion in the study.

A participant or their legally authorized representative must provide written informed consent before any screening tests are performed. A participant's informants/caregivers must also

CONFIDENTIAL

The information contained herein may not be used, disclosed, or published without the written consent of Biogen MA Inc.

provide written informed consent to participate in the study prior to providing any information on either themselves and/or participants. It is preferable that the same informant/caregiver participates and completes the informant/caregiver assessments for the duration of the study.

The Screening Period may be extended up to a total duration of 42 days for eligible individuals who cannot complete the Day 1 Visit within 28 days of signing the ICF.

Part 2 Screening:

For consented participants from Cohorts D1 and D2, the Screening Period for Part 2 begins at the Part 1 Day 169 Visit. Results from Day 169 visit and Day 176 visits may be used for the purpose of screening and do not need to be repeated as long as they are conducted within 1-month of Baseline/loading dose visit (Part 2 Day 1).

For Cohorts A, B, C1 and C2, the Screening Period may be extended up to a total duration of 42 days for eligible individuals who cannot complete the Day 1 Visit within 28 days of signing the ICF (Screening assessments may be performed over multiple days to reduce participant burden.

6.3.2. Retesting

Participants who have a nonclinically significant out-of-range laboratory result can be retested 1 time only at the discretion of the Investigator after discussion with the Sponsor. The Screening Period may be extended up to a total duration of 42 days for eligible individuals who require retesting of laboratory results, including genetic testing results. Individuals who signed the ICF and subsequently do not meet concomitant medication criteria can have their Screening Period extended up to 42 days to ensure that the requirements for concomitant medication stabilization have been met.

The results of the most recent (i.e., obtained at a previous visit) centrally read coagulation tests and platelet count must be reviewed before each LP can be performed. Should the results suggest, in the opinion of the Investigator, that an LP may be safely performed, then no further laboratory values need to be reviewed. However, should, in the opinion of the Investigator, repeat coagulation and platelet tests be clinically indicated, then these tests may be repeated locally to facilitate timely review. Results of any repeat tests must be available before the LP can be performed.

6.3.3. Screen Failures

Screen failures are defined as participants who sign the ICF but are not subsequently randomized. If a participant is considered a screen failure, the reasons for exclusion must be documented in the participant's source documents and on the screening log. Participants who fail screening may be permitted to be rescreened once at the Investigator's discretion after discussion with the Sponsor. All screening assessments would need to be repeated during rescreening except for the following:

A Phase 1/2 MAD Study and Long-Term OLE in Adults With ALS With or Without ATXN2 PolyCAG Expansion

- FSH level in female participants with postmenopausal state confirmed by level obtained in previous screening for this study.
- For participants in Cohorts C2 or D2, confirmation of intermediate (30 to 33) CAG/CAA repeats in at least 1 allele in the ATXN2 gene by the central laboratory, if available from previous screening for this study.

A minimal set of screen failure information is required to ensure transparent reporting of screen failure participants to meet the Consolidated Standards of Reporting Trials publishing requirements and to respond to queries from regulatory authorities. Minimal information includes demography, screen failure details, eligibility criteria, and any SAE.

7. STUDY TREATMENT

7.1. Regimen

In Part 1:

Each participant will receive an IT injection of study treatment (BIIB105 or placebo) over approximately 1 to 3 minutes every 14 days (i.e., Days 1, 15, and 29 in Part 1) during the loading period and every 28 days thereafter up to Day 85 (for Cohorts A, B, C1, and C2) or Day 169 (for Cohorts D1 and D2). Doses of BIIB105 will range from 5 mg up to 120 mg, all formulated in a final volume of mL. Prior to injection, approximately mL of CSF will be collected for analyses. Depending on institutional guidelines, anesthesia or sedation may be used for the LP procedure. Refer to and follow the DHA.

The dosage cannot be modified.

In Part 2:

Participants from Cohorts A, B, C1, and C2 will have a ≥16-week washout period. Participants will receive an IT injection of 60 mg BIIB105 every 14 days (i.e., Part 2 Days 1, 15, and 29) during the unblinded loading period, and every 28 days thereafter up to either Day 729 (Week 104), or until the last participant enrolled has had the opportunity for their Part 2 Day 365 visit (Week 52), whichever occurs later. The 60 mg dose may be increased, at the Sponsor's discretion, to doses up to 120 mg. Before increasing the dose level, the SST must review safety and PK data for Cohort D1 (Part 1) and there must be agreement that the current emerging safety, tolerability, and PK data support the dose increase.

Participants from Cohorts D1 and D2 will not have a washout period and will have a blinded Loading Dose period. Participants who received placebo in Part 1 will receive 3 loading doses of BIIB105 120 mg approximately once every 2 weeks (Days 1, 15, and 29), while participants who received BIIB105 in Part 1 will receive 2 doses of BIIB105 120 mg, on Days 1 and 29, and placebo on Day 15. After the blinded Loading Dose Period, participants from Cohorts D1 and D2 will receive BIIB105 120 mg at each unblinded Maintenance Dose Visit thereafter (either up to Week 104, or until the last participant enrolled has had the opportunity for their Part 2 Day 365 visit [Week 52], whichever occurs later). For participants from Cohort D1 and D2, the first dose for each participant in Part 2 will not occur less than 4 weeks after their last dose in Part 1.

Doses in Part 2 for participants from all cohorts may be decreased at any time in the study at the Sponsor's discretion.

Doses of BIIB105 in Study 275AS101 Part 2 will all be formulated in a final volume of mL. Prior to injection, approximately mL of CSF will be collected for analyses. Depending on institutional guidelines, anesthesia or sedation may be used for the LP procedure. Refer to and follow the DHA.

The dosage cannot be modified.

7.2. Study Treatment Management

Study treatment will be manufactured, handled, and stored in accordance with applicable Good Manufacturing Practice.

Site staff should follow the DHA for specific instructions on the handling, preparation, administration, and disposal of the study treatment.

Study treatment must be dispensed only by a pharmacist or appropriately qualified staff. Study treatment is to be dispensed only to participants enrolled in this study. Once study treatment is prepared for a participant, it can be administered only to that participant. Study treatments are for one-time use only; do not use any study treatment remaining in the vial for another participant.

7.3. Study Treatment

7.3.1. BIIB105

BIIB105 is supplied as a sterile, buffered, and isotonic solution in single-use clear vials containing study treatment either at a concentration of mg/mL and a targeted volume of mL per vial to ensure maximum withdrawal of mL for dose preparation, or at a concentration of mg/mL with a targeted volume of mL per vial to ensure maximum withdrawal of mL for dose preparation (once this presentation is available for use at clinical study sites). This is accompanied by aCSF to be used as diluent where needed. Both BIIB105 and aCSF vials are sealed with a butyl rubber stopper and aluminum over seal with flip-off cap.

The contents of the BIIB105 label will be in accordance with all applicable regulatory requirements. At a minimum, the label will include a study reference code, study treatment identifier, quantity of dosage units, lot number, and other pertinent information in accordance with local law.

7.3.1.1. Preparation

The individual preparing BIIB105 should carefully review the instructions provided in the DHA.

If the packaging is damaged, or if there is anything unusual about the appearance or attributes of the vials or BIIB105, do not use the study treatment. The vial(s) in question should be saved at the study site and the problem immediately reported to the Sponsor.

Contact information for reporting a problem is provided in the study reference guide.

7.3.1.2. Storage

Study treatment must be stored in a secure location.

BIIB105 is to be stored at 2°C to 8°C (36°F to 46°F), in a monitored, locked refrigerator with limited access and protected from light. For the most up-to-date storage requirements, follow the instructions provided in the DHA.

7.3.1.3. Handling and Disposal

The Investigator must return all used and unused vials of BIIB105 as instructed by the Sponsor unless approved for onsite destruction.

If any BIIB105 supplies are to be destroyed at the study site, the institution or appropriate site staff must obtain prior approval from the Sponsor, by providing, in writing, the destruction policy or details of the method of destruction. After such destruction, the Sponsor must be notified, in writing, of the details of the study treatment destroyed (e.g., lot or kit numbers, quantities), the date of destruction, and proof of destruction.

7.3.1.4. Accountability

Accountability for study treatment is the responsibility of the Investigator. The study site must maintain accurate records demonstrating dates and amount of study treatment received, to whom dispensed (participant-by-participant accounting), and accounts of any study treatment accidentally or deliberately destroyed or lost.

Unless otherwise notified, all vials both used and unused, must be saved for study treatment accountability. By the end of the study, reconciliation must be made between the amount of BIIB105 supplied, dispensed, and subsequently destroyed, lost, or returned to the Sponsor. A written explanation must be provided for any discrepancies.

7.3.2. Placebo

Sponsor provided matching placebo is supplied as a sterile, buffered, and isotonic solution in vials. The drug supply label will include conditions for storage, lot number, and other pertinent information.

Placebo is to be stored at 2°C to 8°C (36°F to 46°F), in a monitored, locked refrigerator with limited access and protected from light.

7.4. Blinding Procedures

The Investigator, study staff (except for designated pharmacy staff), and participants will be blinded to the randomized treatment assignments. To maintain the study blind, it is imperative that participant treatment assignments are not shared with the participants, their families, or any member of the blinded study team, both at the site and at the Sponsor and CRO, except the unblinded designated Study Pharmacy Staff and designated Sponsor personnel.

The SST, Biostatistician, Clinical Pharmacologist, and, if required, any ad hoc members, may be unblinded in order to review all safety and available PK data, to assess safety and tolerability, and to make informed decisions regarding dose escalation Section 5.3 and/or for interim analyses of the data.

At the end of the study (i.e., once the clinical study report is finalized), if unblinding will not jeopardize the results of ongoing related studies, the Sponsor will provide the randomization codes to Investigators, who then can inform their participants about the treatment received.

In the event of a medical emergency that requires unblinding of a participant's treatment assignment, refer to Section 12.4.3.1.

7.5. Precautions

Depending on institutional guidelines, anesthesia or sedation may be used for the LP procedure. On dosing days in Part 1, (except Dose 1), participants will remain at the study site for at least 6 hours postdose for safety monitoring. In Part 2, participants who receive the 60 mg dose will remain at the study site for at least one hour postdose, and participants who receive the 120 mg dose will remain at the study site for at least 2 hours postdose for safety monitoring. Participants can be discharged at the discretion of the Investigator and in compliance with the institutional requirements, once the participant has adequately recovered from the dosing procedure. Participants will receive a safety follow-up TC approximately 24 hours after the procedure. During the Follow-up Period, participants will remain under observation in the clinic for approximately 1 hour after the LP procedure and will receive a safety follow-up TC approximately 24 hours after the procedure. Refer to and follow the DHA.

Any antiplatelet or anticoagulant medication that cannot be safely interrupted for an LP procedure, if necessary, according to local or institutional guidelines and/or Investigator determination is prohibited for the duration of the study.

7.6. Compliance

Compliance with treatment dosing is to be monitored and recorded by site staff.

All doses of study treatment will be administered by the site staff.

7.7. Concomitant Therapy and Procedures

7.7.1. Concomitant Therapy

A concomitant therapy is any drug or substance administered between Day 1 and the Final/ET Visit.

Participants should be instructed to contact their Investigators before taking any new medications, including nonprescription drugs and herbal preparations. Use of concomitant medication for symptom management during the study is at the discretion of the Investigator.

7.7.1.1. Allowed Concomitant Therapy

Participants taking concomitant riluzole at study entry must be receiving a stable dose for ≥ 30 days prior to the first dose of study treatment (Day 1) and should remain on this stable dose of riluzole until the Final/ET Visit, unless riluzole use must be discontinued in the judgment of CONFIDENTIAL

The information contained herein may not be used, disclosed, or published without the written consent of Biogen MA Inc.

the Investigator, in which case it should not be restarted during the study. If participants are not receiving riluzole at Part 1 Day 1, they should not initiate it in Part 1.

Participants taking concomitant edaravone at study entry must be receiving a stable dose for ≥ 60 days (2 treatment cycles) prior to the first dose of study treatment (Day 1) and should remain on this stable dose of edaravone until the Final/ET Visit, unless edaravone use must be discontinued in the judgment of the Investigator, in which case it should not be restarted during the study. If participants are not receiving edaravone at Part 1 Day 1, they should not initiate it in Part 1. Edaravone may not be administered on dosing days of this study.

Daily intake of all concomitant medication, vitamins, and supplements should be stabilized at least 14 days prior to Day 1. Doses of vitamins, minerals, and supplements greater than the recommended daily dose should be discouraged during the study.

Supplements that are subject to dose limits from at least 14 days prior to Day 1 and that should remain stable throughout the study are as follows: creatine 5 g/day and vitamin E 1000 IU/day. These daily limits include the total doses obtained through the combination use of daily multivitamins and supplements.

7.7.1.2. Disallowed Concomitant Therapy

Treatment with an antiplatelet or anticoagulant therapy that cannot safely be interrupted for LP according to local standard of care and/or institutional guidelines, in the opinion of the Investigator or Prescriber, should not be taken.

Use of a diaphragm pacing system, investigational drugs other than the investigational product (including drugs for ALS through compassionate use programs), or ASOs is prohibited for the duration of the study.

Use of indwelling injection ports/catheters are prohibited during Part 1 of the study.

Use of approved disease-modifying treatments for ALS other than riluzole or edaravone (i.e., sodium phenylbutyrate and taurursodiol in applicable geographies) is prohibited during Part 1 of the study.

Off-label use of any disease-modifying treatment for ALS is prohibited for the duration of the study.

Participants should be instructed to contact their Investigator before taking any new medications, including nonprescription drugs and herbal preparations.

7.7.2. Concomitant Procedures

A concomitant procedure is any therapeutic intervention (e.g., surgery/biopsy, physical therapy) or diagnostic assessment (e.g., blood gas measurement, bacterial cultures) performed between Day 1 and the Final/ET Visit.

7.8. Continuation of Treatment

There is currently no provision to provide study treatment after the study.

8. RULES FOR DISCONTINUATION OF STUDY TREATMENT AND WITHDRAWAL FROM STUDY FOR INDIVIDUAL PARTICPANTS

8.1. Discontinuation of Study Treatment

A participant must permanently discontinue study treatment for any one of the following reasons:

- The participant becomes pregnant. Report the pregnancy according to the instructions in Section 12.4.1.
- The participant withdraws consent to continue study treatment.
- The participant experiences an AE that necessitates permanent discontinuation of study treatment.
- The participant experiences a medical emergency that necessitates unblinding of the participant's treatment assignment.
- The participant is unwilling or unable to comply with the protocol.
- At the discretion of the Investigator for medical reasons.
- At the discretion of the Sponsor.

The primary reason for discontinuation of study treatment must be recorded in the participant's CRF.

If a participant received a dose of study treatment, then he or she will be encouraged to complete all the scheduled safety evaluations during the ET Visit.

Participants who discontinue treatment are encouraged to remain in the study and continue protocol-required tests and assessments, where possible.

8.2. Lost to Follow-Up

Participants will be considered lost to follow-up if they repeatedly fail to return for scheduled visits and are unable to be contacted by the study site.

The following actions must be taken if a participant fails to return to the clinic for a required study visit:

• The site must attempt to contact the participant, reschedule the missed visit as soon as possible, counsel the participant on the importance of maintaining the assigned visit

schedule, and ascertain whether the participant wishes to and/or should continue in the study.

- In cases in which the participant is deemed lost to follow-up, the Investigator or designee must make every effort to regain contact with the participant. These contact attempts should be documented in the participant's medical record.
- Should the participant continue to be unreachable, that participant will be considered to have withdrawn from the study with a primary reason of lost to follow-up.

8.3. Withdrawal of Participants From the Study

Participants must be withdrawn from the study for any one of the following reasons:

- The participant withdraws consent for participation in the study.
- The participant enrolls into another interventional clinical study in which an investigational treatment or approved therapy for investigational use is administered.
- The participant is unwilling or unable to comply with the protocol.

The primary reason for the participant's withdrawal from the study must be recorded in the participant's CRF.

Participants who withdraw from the study prior to completing study follow-up (last visit) in Part 1 may be replaced at the same dose cohort, at the discretion of the Sponsor.

After withdrawal from the study, follow-up on vital status and date of death (if deceased) will be performed for participants who provide optional consent for data collection after study withdrawal.

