11.2.11. Collection of Vital Status Before and After Study Withdrawal or Completion

Participants' vital status will be collected throughout the study. For participants who provide optional consent for data collection after study withdrawal or completion, follow-up on vital status and date of death (if deceased) will be performed.

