16.6. Public Health Emergencies

In the event of a public health emergency that results in site closure, travel restrictions, and/or the study being deprioritized at the site such that clinic visit(s) cannot occur, a protocol deviation would be incurred for any deviation from the protocol-specified visits and assessments, with additional notation that this protocol deviation is due to the public health emergency. If a protocol-specified clinical visit cannot occur because of a public health emergency, the following mitigating options should be pursued (if allowed per local regulations), in order of preference (in which the highest preference option that is feasible should be done): 1) transfer to another active study site that is open, 2) home visit, 3) telemedicine visit (e.g., by telephone or web conference), and 4) local laboratory visit. These mitigating options only apply in the setting of a public health emergency in which a protocol-specified clinic visit cannot occur and should not be pursued solely because of a participant's preference. If the participant does not participate in one of these options, a Safety Telephone call must be conducted within 14 days of the last dosing visit.

A third-party vendor has been engaged to perform assessments at the study participant's home, which may include but are not limited to:

- Limited neurological examination
- Physical examination
- Vital signs
- Height and body weight collection
- •
- •
- •
- C-SSRS
- SVC
- Biological sample collection

A Phase 1/2 MAD Study and Long-Term OLE in Adults With ALS With or Without ATXN2 PolyCAG Expansion

- Pregnancy test (if applicable)
- HHD
- Collection/shipment of ventilation diary records

The following assessments will be performed via telephone (telemedicine) by the site staff:

- ALSFRS-R
- Review of concomitant medications and AEs

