5.9. Pharmacodynamic and biomarker Endpoints

No pre-specified analyses of pharmacodynamic and biomarker endpoints will be performed for this analysis because there will be no new pharmacodynamic and biomarker data beyond

CONFIDENTIAL

The information contained herein may not be used, disclosed, or published without the written consent of Biogen MA Inc.

what was available for the interim analysis will be available. Future analyses may be performed post-hoc.

CONFIDENTIAL

The information contained herein may not be used, disclosed, or published without the written consent of
Biogen MA Inc.

6. Changes from Protocol-Specified Analyses

- Time to death, incorporating post-study withdrawal or study completion vital status data will not be performed as post-study withdrawal vital status data will not be collected at the time of this analysis.
- Add time to event endpoint of time to death, permanent ventilation (≥ 22 hours of mechanical ventilation [invasive or noninvasive] per day for ≥ 21 consecutive days), or withdrawal from study due to disease progression.

7. References

Protocol 275AS101 Protocol Version 5.0 275AS101 Unblinding Plan Version x.0

A horizontal bar chart consisting of four solid black bars of increasing height from left to right. The bars are separated by small gaps and are set against a white background.

CONFIDENTIAL

The information contained herein may not be used, disclosed, or published without the written consent of Biogen MA Inc.

CONFIDENTIAL

The information contained herein may not be used, disclosed, or published without the written consent of
Biogen MA Inc.

Signature Page

Document Name:

BIIB105_275AS101_FINAL_Part2_Integrated_CSR_Final_Statistical_Analysis_Plan_v1.0

Document Title: A Phase 1/2 Multiple Ascending Dose Study With a Long-Term Open-Label Extension to Assess the Safety, Tolerability, Pharmacokinetics, Pharmacodynamics, and Effect on Disease Progression of BIIB105 Administered Intrathecally to Adults With Amyotrophic Lateral Sclerosis With or Without PolyCAG Expansion in the ATXN2 Gene

Signed by	Role	Date / Time (UTC)
██████████	Signing as Approver	05-Sep-2024 16:18:52
██████████	Signing as Approver	05-Sep-2024 23:37:12
██████████	Signing as Author	05-Sep-2024 13:57:55

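### Protocol 8.1 and 8.3 attach incompatible consequences to the same inability to comply; read literally, 8.3 ends functional and ventilation follow-up for a reason that may reflect progression

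*Protocol*

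**What the plan says.** Protocol 8.1 opens with "A participant must permanently discontinue study treatment for any one of the following reasons", and one of its reasons is "The participant is unwilling or unable to comply with the protocol". It then adds: "Participants who discontinue treatment are encouraged to remain in the study and continue protocol-required tests and assessments, where possible".

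Protocol 8.3 opens with "Participants must be withdrawn from the study for any one of the following reasons", and the same compliance reason appears again, word for word. After withdrawal, 8.3 provides that "follow-up on vital status and date of death (if deceased) will be performed for participants who provide optional consent for data collection after study withdrawal"; section 11.2.11 repeats this. No continued functional or ventilation assessment is described.

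Home and telephone visits appear in Protocol 16.6, but "These mitigating options only apply in the setting of a public health emergency in which a protocol-specified clinic visit cannot occur".

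Protocol 13.3.5 plans a separate time-to-death analysis that uses post-withdrawal vital status. Section 6 of the final SAP (Part 2 and integrated, September 2024) drops it because "post-study withdrawal vital status data will not be collected at the time of this analysis". The same section adds a composite of death, permanent ventilation, or study withdrawal due to disease progression.

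**The concern.** One participant can satisfy both rules at once, and the rules disagree on whether data collection continues. ALS takes away strength and function, and every dose is given by lumbar puncture, so inability to keep to the protocol may itself be a sign of progression. If sites follow 8.3, the chance of having missing data then depends on the outcome being measured.

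At stake are the secondary endpoints of the integrated analysis: ALSFRS-R, SVC, HHD, and the survival endpoints. Multiple imputation from observed values does not correct for decline that those values do not predict. Censoring at the last date known alive assumes that people who leave have the same later risk as those who stay. If they do worse, decline and deaths are understated. If they leave at different rates by arm, the functional comparison is biased as well.

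**Working it through.** **Step 1: the two rules side by side.**

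| | Protocol 8.1 | Protocol 8.3 |
|---|---|---|
| What is mandatory | stopping study treatment | leaving the study |
| Compliance ground | unwilling or unable | identical words |
| Consent ground | consent to treatment | consent to participation |
| Afterwards | assessments encouraged | vital status only, if optional consent is given |

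The consent row separates treatment from study; the compliance row does not. Because 8.3 is mandatory and the stay in 8.1 is only encouraged, a site that applies both literally withdraws the participant.

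**Step 2: what happens to each outcome after an 8.3 withdrawal.**

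- ALSFRS-R, SVC, HHD: not collected. Final SAP 5.6.1 imputes missing post-baseline values by treatment group from riluzole/edaravone use, the baseline value and all available post-baseline values. These data feed the Week 40 early-start versus delayed-start contrasts (5.6.2 to 5.6.4).
- Permanent ventilation: the weekly diary and the site record stop.
- Death: collected only with optional consent and not used in the final SAP. Section 5.6.5 censors event-free participants at the interim cut date or the last date with evidence that they were alive.
- Added composite: captures the withdrawal if progression is the recorded reason. Progression is not one of the three grounds in 8.3, and the documents do not show how a site would code a progression-related inability to comply.

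**Step 3: possible size.** The plan states no figure to reproduce, and neither document gives withdrawal counts by reason. All inputs below are assumptions.

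*Mortality.* Let a share p = 0.15 be withdrawn uniformly between Weeks 8 and 40, with 1-year mortality 0.40 against 0.106 in the rest, and exponential survival.

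- Weekly hazards: h1 = -ln(0.60)/52 = 0.00982; h0 = -ln(0.894)/52 = 0.00215.
- True 52-week risk: 0.15 x 0.40 + 0.85 x 0.106 = 0.150.
- Let G(t) be the fraction of the withdrawn group still followed: 1 up to Week 8, falling linearly to 0 at Week 40. The hazard that Kaplan-Meier sees is h(t) = [p h1 S1 G + (1-p) h0 S0] / [p S1 G + (1-p) S0], and its risk is 1 - exp(-integral of h from 0 to 52) = 0.129. A simulation of 400,000 participants agrees.
- Understatement: 15.0% - 12.9% = 2.1 percentage points.
- With p from 5% to 20%, mortality in the withdrawn group from 20% to 60%, and 10.6% in the rest, it runs from about 0.3 to 4.3 points.
- If true risk is held at 15.0% and this ground accounts for only 5% of participants at 40% mortality, the rest have (0.150 - 0.05 x 0.40)/0.95 = 13.7% and Kaplan-Meier gives 14.3%. At 2%, the rest have (0.150 - 0.02 x 0.40)/0.98 = 14.5% and it gives 14.7%.

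*Function.* Let w be the withdrawn share in an arm and D the number of ALSFRS-R points by which those withdrawn are worse than imputed. The arm mean is too favourable by wD, and the contrast shifts by the difference in wD between arms.

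- Withdrawal differing by 10 percentage points, D = 3 to 5 in both arms: 0.10 x 3 = 0.3 to 0.10 x 5 = 0.5 points, in favour of the arm with more withdrawals.
- Equal w and equal D: no shift in the contrast. With w = 0.15, decline is still understated in each arm by 0.15 x 3 = 0.45 to 0.15 x 5 = 0.75 points.

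**The case against.** It can fairly be said that the two sections are meant for different people: 8.1 for those who cannot be dosed, 8.3 for those who cannot take part at all. Other text fits that reading. Protocol 8.2 has sites reschedule a missed visit before giving up. Final SAP 5.6.1 uses all assessments from participants who missed doses, and 5.6.3 scores an HHD muscle that cannot be tested as zero instead of losing it. This makes automatic withdrawal less likely in practice. But both bullets refer to the protocol as a whole, and no sentence draws the distinction, so the contradiction stands.

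Several stronger readings are tempting, and the objection to each succeeds:

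- *That 8.3 ends survival follow-up.* It does not. Sections 8.3 and 11.2.11 keep vital status and date of death for those who give optional consent.
- *That 8.3 is why the final SAP omits post-withdrawal deaths.* The stated reason is that those data will not have been collected by then, in an abbreviated analysis after early termination by the sponsor. Rewording 8.3 would not by itself restore that analysis.
- *That every survival endpoint is censored just before high risk.* The added composite counts a withdrawal recorded as due to disease progression. Time to death and time to death or permanent ventilation remain exposed.
- *That the most disabled participants are the ones removed.* Inability is undefined, and no withdrawal counts by reason are given.

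It is also true that the primary endpoints are adverse events, that the imputation already conditions on each participant's own earlier scores, so D could be small, and that no bias in a survival comparison between arms has been shown.

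**Conclusion.** The point holds as an unresolved contradiction with a plausible, unquantified consequence. The same trigger leads to continued assessment in 8.1 and mandatory exit in 8.3. Following 8.3 discards functional and ventilation data, and makes vital status conditional, for a reason that may be related to outcome. The analysis offsets this only in part.

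The documents do not support a numerical claim about this trial. The 2.1-point mortality gap and the 0.3 to 0.5 point ALSFRS-R shift show what could happen. The first depends on how many leave on this ground and how much worse they do. The second also needs unequal withdrawal between arms, or unequal deviation from imputation. The mortality figure is a single-group level, not a treatment effect. Early termination limits what can still be recovered in this study but does not remove the inconsistency.

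**What to change.** Reconcile 8.3 with 8.1. Either delete the compliance bullet from 8.3, or limit it to participants who can no longer provide any data. Those unable to comply then stay in the study for whatever assessments remain possible, including vital status. Deletion leaves no gap: unwilling participants can withdraw consent under 8.3, and unreachable ones fall under 8.2. The treatment rules in 8.1 do not change.

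The cost is protocol wording, with the small downside of some partial follow-up data. Remote assessment outside public health emergencies is optional and not needed for this fix. It would need its own text, because 16.6 covers telephone ALSFRS-R and review of medications and adverse events, but not a telephone ventilation review or a vital-status call.

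For reporting, final SAP 5.2 already tabulates withdrawal reasons by Part 1 assignment for Cohorts D1 and D2. Showing the inability-to-comply exits there as a separate reason would replace the assumed shares above with observed ones.
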